9.4 Questionnaires

Trained Users and Untrained Users will complete NASA TLX questionnaires soon after each simulation, and all participants (Trained Users, Untrained Users and PWDs) will complete further questionnaires at the end of the study.

For the end-of-study questionnaires, the questionnaire directly comparing both devices will always be given first. The order of the NG- and GEK-specific questionnaires will be randomized.

NASA Task Load Index

Following each simulation, Trained Users and Untrained Users (but not PWDs) will be asked to complete Hart and Staveland's NASA TLX to gauge their experience during that simulation. The NASA TLX is a series of 21-point scales that measure various aspects of carrying out a task. Example questions include Mental Demand ("How mentally demanding was the task?"), Effort

(“How hard did you have to work to accomplish your level of performance?”) and Frustration (“How insecure, discouraged, irritated, stressed, and annoyed were you?”).

Following each simulation, Trained Users and Untrained Users (but not PWDs) will be asked to complete Hart and Staveland’s NASA TLX to gauge their experience during that simulation. The NASA TLX measures the perceived impact of carrying out a task in 6 dimensions (scales):

- Mental Demand (“How mentally demanding was the task?”)
- Physical Demand (“How physically demanding was the task?”)
- Temporal Demand (“How hurried or rushed was the pace of the task?”)
- Performance (“How successful were you in accomplishing what you were asked to do?”)
- Effort (“How hard did you have to work to accomplish your level of performance?”)
- Frustration (“How insecure, discouraged, irritated, stressed, and annoyed were you?”).

For each of these scales, the subject assigns as **score** using a visual analogue scale divided into 20 segments using 21 hashes. This 21-point scale (0-20) will be converted to a 0-100 point scale for the analysis.

Additionally, **weights** will be calculated for each the scales. This will be carried out using comparison cards, on which each scale is compared to the 5 other scales, creating a total of 15 comparison cards. The subject needs to choose, for each comparison, which scale was the most demanding for the task. For each time a scale was selected by the subject, a value of 1 is added to its weight. As each scale is compared to the other 5 scales exactly ones, the maximum of the weight is 5 (this scale was always selected as being the most demanding) and the minimum is zero (this scale was never selected as being the most demanding).

For the analyses, a weighted average of the 100-point-scale scores will be computed in the analysis datasets for each subject and administration method (NG / GEK).

Questionnaire Comparing Both Devices

For Trained Users and Untrained Users, the comparative questionnaire will include questions on preference, ease of use and confidence using each device.

Person with diabetes will receive a differently worded questionnaire that will include questions on their preference of device, and their impression of the user experience for ease of use and confidence.

Device-Specific Questionnaires (NG and GEK)

All participants (Trained Users, Untrained Users and PWDs) will answer 2 device-specific questionnaires, regarding NG and GEK individually. These will include questions related to ease of use and confidence in using each device, without comparing to the other device.

All questionnaire data will be listed and summarized by part and treatment. For Part A (Trained Users), summaries will also be stratified between those users who have an accompanying PWD with T1DM, those who have an accompanying PWD with T2DM and overall.

9.5 Statistical Methodology

The following endpoints will be summarized by treatment using descriptive statistics and listed:

- The percentage of Trained Users and Untrained Users that perform a successful administration
- The time taken by Trained Users and Untrained Users to successfully administer NG or GEK
- The percentages of Trained Users and Untrained Users who complete all of the critical steps
- The percentage of all simulations that result in a successful administration of NG, for all users combined
- The average length of time taken by PWDs to teach the use of NG and GEK to their associated Trained User,

The McNemar test will be used to assess the percentage of Trained Users that perform a successful administration. The exact-sign test will be used as a sensitivity analysis.

Successful administration will be assessed, for each cohort:

- NG (Trained User) versus GEK (Trained User)
- NG (Untrained User) versus GEK (Untrained User)

Example SAS code for the McNemar test

```
proc freq data = success;
  weight count / zeros;
  tables NG_trained*GEK_trained / agree;
  exact mcnem;
run;
```

Example SAS code for the exact-sign test

```
proc univariate data=success;
  var success_diff;
run;
```

Where `success_diff` is 1 if NG is successful and GEK is not, 0 if both treatments are successful or not successful and -1 if NG is not successful and GEK is successful.

For Part A (Trained Users), assessment of successful administration will also be stratified between those users who have an accompanying PWD with T1DM, and those who have an accompanying PWD with T2DM.

Time to administer a dose will be assessed using summary statistics, making the following comparisons:

- NG (Trained User) versus NG (Untrained User) – two sample t-test
- GEK (Trained User) versus GEK (Untrained User) – two sample t-test

- NG (Trained User) versus GEK (Trained User) – Paired t-test
- NG (Untrained User) versus GEK (Untrained User) – Paired t-test

This analysis, using descriptive statistics and the appropriate t-test, will be assessed for successful and unsuccessful administration combined, as well as successful administration only. Time needed to complete glucagon administration will be shown categorically based on the following categories:

- <30 seconds
- 30 seconds-45 seconds
- 45 seconds-1 minute
- 1 minute-1 minute 15 seconds
- 1 minute 15 seconds-1 minute 30 seconds
- 1 minute 30 seconds-1 minute 45 seconds
- 1 minute 45 seconds-2 minutes
- 2 minutes-2 minutes 15 seconds
- 2 minute 15 seconds-2 minutes 30 seconds
- 2minutes 30 seconds-2 minutes 45 seconds
- 2 minutes 45 seconds-3 minutes
- 3-4 minutes
- 4-5 minutes
- 5-10 minutes
- >10 minutes

A graphical presentation of the successful administration times will be provided using a Kaplan-Meier plot.

To simultaneously model the training effect (Trained Users versus Untrained Users) and the treatment effect (NG versus GEK), a generalized estimating equations (GEEs) model will be performed, with treatment, training and the treatment-by-training interaction effect as independent variables, and the participant as participant identifier. As each Trained User and Untrained User will perform both the NG and the GEK administration, the data are paired for the device type but not paired for the level of training. Using a GEE model will enable estimation of both effects simultaneously, and also estimation of the interaction effect, which will test whether the difference between devices varies between Trained Users and Untrained Users. Furthermore, the randomization order (NG-GEK versus GEK-NG) can be tested within this model. Given the low sample size of this study and multitude of variables that can be entered, this GEE modelling will be exploratory in nature.

Primarily, a GEE model using the binary distribution (success versus no success) and the identity link will be produced: this will produce estimated rate differences with 95% confidence intervals. In case this model fails to converge, log or logit links can be attempted, to estimate relative risks or odds ratios, respectively.

Example SAS code:

```
proc genmod data=xx descending;
class subjid arm trt ftrt ;
model success = arm|trt ftrt / link=identity dist=bin;
repeated subject=subjid;
lsmeans arm*trt / ilink diff;
lsmeans arm / ilink diff;
lsmeans trt / ilink diff;
lsmeans ftrt / ilink diff;
run;
```

where arm = trained or untrained, trt = NG or IM and ftrt = first treatment received

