10.3. Statistical Analyses

Statistical analysis of this study will be the responsibility of Eli Lilly and Company or its designee.

The McNemar test will be used to assess the primary objective of the study (Section 4). The exact-sign test will be used as a sensitivity analysis for the primary objective.

Successful administration will be assessed, for each cohort:

- NG (Trained User) versus GEK (Trained User)
- NG (Untrained User) versus GEK (Untrained User)

For Part A (Trained Users), assessment of successful administration will also be stratified between those users who have an accompanying PWD with T1DM, and those who have an accompanying PWD with T2DM.

For baseline data, continuous variables will be presented using simple descriptive statistics such as mean, standard deviation, median and range. Categorical variables will be presented as n/N and percentage.

Time to administer a dose will be assessed, making the following comparisons:

- NG (Trained User) versus NG (Untrained User)
- GEK (Trained User) versus GEK (Untrained User)
- NG (Trained User) versus GEK (Trained User)
- NG (Untrained User) versus GEK (Untrained User)

This analysis, using descriptive statistics, will be assessed for successful and unsuccessful administration combined, as well as successful administration only. Time needed to complete glucagon administration will be shown categorically. A graphical presentation of the successful administration times may be provided.

To simultaneously model the training effect (Trained Users versus Untrained Users) and the treatment effect (NG versus GEK), a generalized estimating equations (GEEs) model will be performed, with treatment, training and the treatment-by-training interaction effect as independent variables, and the participant as participant identifier. As each Trained User and Untrained User will perform both the NG and the GEK administration, the data are paired for the device type but not paired for the level of training. Using a GEE model will enable estimation of both effects simultaneously, and also estimation of the interaction effect, which will test whether the difference between devices varies between Trained Users and Untrained Users. Furthermore, the randomization order (NG-GEK versus GEK-NG) can be tested within this model. Given the low sample size of this study and multitude of variables that can be entered, this GEE modeling can be exploratory in nature.

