7. SAMPLE SIZE JUSTIFICATION

The sample size is 26 in each of the 2 cohorts (Trained Users and Untrained Users). It is assumed that the percentages of successful dosing of NG and GEK will be 90% and 50%, respectively.

Additionally, a proportion of discordant pairs of 45% is assumed, which reflects a moderate within-subject correlation between the 2 treatments.

These numbers are based on the Yale 2017 study³, where 15 out of 16 (93.8%) NG simulations were completely successful and 8/16 (50%) GEK administrations were partially or completely successful in the “caregivers” group (the equivalent of the Trained Users group in this study). Note that for GEK, the “partial or complete success” rate is used. In Yale 2017, only 2 out of 16 (12.5%) simulations were completely successful for the GEK treatment. Hence, we are using a best-case scenario approach for the successful administration rates of GEK in the current study. In conclusion, the 90% success rate for NG is based on the Yale 2017 NG success rate (15/16, 93.8%, rounded down) and the 50% success rate for GEK is based on the best-case scenario from the Yale 2017 study, i.e. partial administration of GEK in 8/16 (50%) simulations.

Based on these numbers, the sample size will provide 90% statistical power to detect a statistically significant difference between success rates of NG and GEK, using the test with a 2-sided alpha level of 0.05.

Enrollment will be continued per group until 26 Trained Users have been recruited (stratified into 13 who have an accompanying PWD with T1DM, and 13 who have a PWD with T2DM) and 26 Untrained Users have been recruited.

Participants who are randomized but do not participate in the study simulations may be replaced to ensure that enough participants may complete the study.

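### The primary McNemar test is not fixed as asymptotic or exact, and its only named sensitivity analysis repeats the exact McNemar p-value

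*SAP*

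**What the plan says.** For the primary objective, SAP 9.5 states: "The McNemar test will be used to assess the percentage of Trained Users that perform a successful administration". It does not say whether the large-sample or the exact version is meant. The example code has the table statement "tables NG_trained*GEK_trained / agree", which gives the asymptotic McNemar statistic, followed by an `exact mcnem` statement, which gives the exact p-value.

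Protocol 10.3 says "The exact-sign test will be used as a sensitivity analysis for the primary objective", and SAP 9.5 repeats this: "The exact-sign test will be used as a sensitivity analysis". The SAP runs the test on a variable, `success_diff`, that "is 1 if NG is successful and GEK is not, 0 if both treatments are successful or not successful", and -1 in the opposite case. No other sensitivity analysis is named for the primary endpoint. SAP 8 defines a Per Protocol Population, but no section attaches it to the primary comparison.

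Order of devices appears once among the analyses. In the GEE model, "the randomization order (NG-GEK versus GEK-NG) can be tested within this model". The example code includes first treatment (`ftrt`) as a main effect. SAP 9.5 calls the GEE exploratory, and the model pools Trained and Untrained Users.

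The sample-size text (Protocol 10.1, SAP 7) claims 90% power for 26 pairs at two-sided 0.05. It too leaves the version of the test open.

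**The concern.** There are two linked problems.

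First, a decision rule with two possible answers is not a fixed rule. With about 12 discordant pairs expected (0.45 × 26 = 11.7), the chi-square approximation and the exact binomial can differ enough to matter near 0.05. If they disagree, the choice would be made after the data are seen, although SAP 3 requires sign-off before the first simulation.

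Second, a sensitivity analysis should show whether the conclusion survives a change of assumption. The sign test uses the same discordant pairs, the same null hypothesis and the same binomial reference distribution as exact McNemar. It says nothing about missing simulations, choice of population or order of devices. A report that the primary result was confirmed by the exact-sign test would claim more support than it has.

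**Working it through.** **Inputs** (SAP 7, Protocol 10.1): n = 26 pairs; success 90% (nasal) and 50% (kit); discordant pairs 45%; two-sided alpha 0.05. Let p10 be the probability that only nasal succeeds and p01 that only the kit succeeds. From p10 + p01 = 0.45 and p10 - p01 = 0.40, p10 = 0.425 and p01 = 0.025.

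**1. The plan's own power figure.** The Connor formula gives

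power = Φ[(d√n - 1.96√pd) / √(pd - d²)] = Φ[(0.40√26 - 1.96√0.45) / √(0.45 - 0.16)] = Φ[(2.040 - 1.315) / 0.539] = Φ(1.346) = 91.1%.

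The n required for 90% is 25.1, rounded up to 26, so the stated figure is reproduced. Enumerating every outcome at n = 26 gives 90.8% for exact McNemar and 94.8% for asymptotic. The smallest n reaching 90% is 26 for the exact test (25 gives 89.3%) and 22 for the asymptotic test (90.4%).

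**2. Sign test against exact McNemar.** Let b pairs favour nasal and c favour the kit, with m = b + c.

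- Exact McNemar: p = min(1, 2·P[Bin(m, 0.5) ≤ min(b, c)]).
- Sign test: zeros drop out, leaving m non-zero differences, and p = min(1, 0.5^(m-1)·Σ C(m, j) for j = 0 to min(b, c)).

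These are the same expression. For 7:1 both give 2 × (1 + 8)/256 = 0.070. Over all 378 possible (b, c) tables with 26 pairs, the largest difference is 1e-16, which is rounding.

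**3. Where the two McNemar p-values part.** The asymptotic p-value refers (b - c)²/(b + c) to chi-square on 1 degree of freedom. For 7:1 that is 36/8 = 4.5, p = 0.034. Examples of splits on opposite sides of 0.05:

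| Discordant split | Asymptotic p | Exact p |
|---|---|---|
| 4:0 | 0.046 | 0.125 |
| 5:0 | 0.025 | 0.063 |
| 7:1 | 0.034 | 0.070 |
| 9:2 | 0.035 | 0.065 |
| 11:3 | 0.033 | 0.057 |

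The same happens at 12:4, 14:5, 15:6, 16:6, 17:7 and 18:8. In each case the asymptotic test is significant and the exact test is not.

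**4. How often.** Summing the multinomial probabilities at the planning values gives 3.99%. This equals the power gap, 94.79% - 90.81%, as it must when every disagreement goes the same way. Away from the planning values, which is an assumption:

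- True difference 25 or 30 points, 45% discordant: 9.6% or 9.7%.
- Nasal 90%, outcomes independent, kit 40%, 30% or 12.5%: 1.8%, 0.3% or about 0.0005%. The 12.5% is the complete-success rate that the sample-size text reports for the kit in the earlier simulation study.

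**5. Type I error at n = 26.** At 45% discordance it is 2.4% exact and 4.3% asymptotic. Over discordance rates from 5% to 100% in steps of 5 points, exact never exceeds 3.3%. Asymptotic passes 5% from 65% discordance upward and reaches 5.6% at 95%, and 7.6% at the extreme of 100%.

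**6. Order.** Assume 13 pairs per schedule (the documents give no allocation ratio), no device effect and 45% discordance. Let the chance that the success in a discordant pair falls in the second simulation rise from 0.5 to 0.9. Type I error falls from 2.4% to 0.8% (exact) and from 4.3% to 1.7% (asymptotic).

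**The case against.** The strongest reply is that the plan does rank its tests. The ordinary reading is a chi-square McNemar as primary, checked by an exact test. With about 12 discordant pairs that is a sensible check, and by the figures above it would change the verdict in 4.0% of trials. On this view `exact mcnem` is a spare line in code labelled as an example, and only one word, asymptotic or exact, is missing. This stands in part: the sign test cannot be called worthless. But neither document says that the asymptotic test is primary, and the code produces the exact p-value under the McNemar name.

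A second reply is that 4.0% may overstate the risk. The plan itself calls 50% a best case for the kit, based on partial success, and the disagreement shrinks quickly as that rate falls. This also stands. The opposite risk, a smaller true difference, raises it to about 10%.

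A reader might infer that ignoring order biases the primary comparison, since the second simulation follows practice in the first. The documents do not support that. Order is randomized, and with balanced schedules a period effect makes McNemar conservative. Nor is order absent from the plan, because the GEE code carries `ftrt`. That term is a sequence contrast in an exploratory pooled model. It does not adjust the Trained User comparison for period, which would need a period term or a treatment-by-`ftrt` interaction.

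**Conclusion.** The point holds. Two McNemar p-values are requested, neither is named as decisive, and the only named sensitivity analysis equals one of them exactly. The redundancy is certain: it follows from the formulas and the coding of `success_diff`. That the code prints both p-values rests on standard SAS behaviour, since the documents show only the statements.

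The practical size is modest. The verdict would depend on the choice in 4.0% of trials at the planning values, in about 10% if the true difference is 25 to 30 points with 45% discordance, and almost never if kit success is far below 50%. The stated 90% power is met by either version at 45% discordance. That figure matters: at 50% discordance, the value under independent outcomes, power is 83.9% exact and 89.4% asymptotic.

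This should be corrected before the data are seen. It does not show that the primary test is invalid or the trial too small.

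**What to change.** 1. In SAP 9.5, name the exact two-sided McNemar p-value as the one that decides the primary objective, and label the asymptotic value descriptive or remove it. The sample size stays at 26. The cost is about 4 points of power against the asymptotic test (90.8% v 94.8%). The gain is type I error below 5% at every discordance rate checked.
2. Drop the exact-sign test as the sensitivity analysis and replace it with one that changes an assumption. One option is the Mainland-Gart test: Fisher's exact test on the discordant pairs, cross-classified by Schedule I or II and by which simulation succeeded. Its power at the planning values is about 87% (86.9%, assuming 13 per schedule and no period effect). It should be labelled supportive, because it can miss significance when the primary test does not. Reasonable alternatives are to count missing simulations as failures, or to repeat the primary test in the Per Protocol Population.
3. Tabulate success by device within each schedule.

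All of this needs only SAP wording, a few lines of code and one small table. No data collection changes.

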3.3. Benefit/Risk Assessment

This study does not involve the dosing of study drug to humans. As such, there is no expected benefit to study participants. During each simulation with a GEK, there is a risk that participants may suffer a needle-stick injury, which may also result in accidental administration of the marketed comparator product. Site staff will closely monitor simulations and respond to any such safety issues that arise.

4. Objectives and Endpoints

Table IGBM.1 shows the objectives and endpoints of the study.

Table IGBM.1. Objectives and Endpoints

Objectives	Endpoints
Primary	
To test the hypothesis that more Trained Users can successfully administer NG than GEK when treating a simulated episode of severe hypoglycemia.	The percentage of Trained Users that perform a successful administration (complete dose delivered and all critical steps completed), both for NG and GEK. See Section 5.1.3.4 for definitions of complete dose and critical steps.
Secondary	
To test the hypothesis that more Untrained Users can successfully administer NG than GEK when treating a simulated episode of severe hypoglycemia.	The percentage of Untrained Users that perform a successful administration (complete dose delivered and all critical steps completed), both for NG and GEK. See Section 5.1.3.4 for definitions of complete dose and critical steps.
To compare the average time to successfully administer NG, compared with GEK.	The time taken by Trained Users and Untrained Users to successfully administer NG or GEK (complete dose delivered and all critical steps completed), as measured by site staff.
To compare percentages of users who complete critical administration steps for both NG and GEK.	The percentages of Trained Users and Untrained Users who complete all of the critical steps for both NG and GEK, as assessed by site staff.
To assess the number of simulations that result in successful administration of NG.	The percentage of all simulations that result in a successful administration of NG, for all users combined.
To assess whether, overall, one device (NG or GEK) is preferred over the other.	The percentage of participants (Trained Users, PWDs and Untrained Users) that prefer one device over the other, as recorded in a questionnaire.
To assess overall ease of use of both devices (NG and GEK).	The 'ease of use' questionnaire ratings given to NG and to GEK by Trained Users, PWDs and Untrained Users.

Objectives	Endpoints

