5.1.3.1. Part A (Trained Users)

Trained Users will be required to attend the study site on 3 occasions, each time accompanied by the PWD with whom they are associated.

At **Visit 1**, each Trained User and their associated PWD will be evaluated for eligibility, give informed consent, and be randomized to 1 of 2 schedules ([Table IGBM.2](#)).

Randomization will be stratified by the type of diabetes, i.e. randomization will be performed separately for PWDs with type 1 diabetes mellitus (T1DM) and type 2 diabetes mellitus (T2DM), and their accompanying Trained User.

Following randomization, site staff will instruct the PWD how to use Device 1 (i.e. either NG or GEK, depending on the randomization). This instruction will include a mock administration, during which the PWD will actuate the device. After a "memory decay" period including a distractor task (see Section [5.1.3.5](#)), the PWD will relay instructions on how to use Device 1 to the Trained User.

At **Visit 2**, approximately 7 days after Visit 1, each Trained User will take part in a simulation of a severe hypoglycemia emergency with a manikin (see Section [5.1.3.3](#)). The gender of the manikin will match the gender of the PWD. The PWD will not be in the room and will not observe the simulation. Site staff will assess dose administration (successful/unsuccessful; see Section [5.1.3.4](#)), and the time taken to administer a dose.

After a short rest period, the Trained User will complete the NASA TLX questionnaire about their experience with Device 1. At around the same time, site staff will instruct the PWD how to use Device 2. After a "memory decay" period including a distractor task (see Section [5.1.3.5](#)), the PWD will relay instructions on how to use Device 2 to the Trained User.

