5.1.3.2. Part B (Untrained Users)

Untrained Users will attend the site for 2 visits ([Figure IGBM.2](#)).

At **Visit 1**, after being evaluated for eligibility and giving informed consent, each Untrained User will be randomized to 1 of 2 schedules ([Table IGBM.2](#)), which will determine the device used at each simulation. Male manikins will be used in each case.

Each Untrained User will be given a brief explanation of diabetes and severe hypoglycemia, and briefly shown an example of Device 1 (NG or GEK depending on randomization). No instruction will be given on how to use the device; nor will the Untrained User be allowed time to read any instructions for using the device.

Each Untrained User will then take part in a simulation (see Section [5.1.3.3](#)) using Device 1. Staff will assess successful or unsuccessful treatment (Section [5.1.3.4](#)), and time to successful administration (if this occurred within the allotted time). After a short rest period, the Untrained User will complete the NASA TLX questionnaire about their experience.

At **Visit 2**, approximately 7 days after Visit 1, each Untrained User will be shown an example of Device 2. As at Visit 1, no instruction will be given on how to use the device. The Untrained User will take part in a simulation using Device 2, and then complete the NASA TLX. Site staff will assemble a video of both simulations, and the Untrained User will watch it. After a delay of 55 to 60 minutes, the Untrained User will fill in a questionnaire comparing both devices, and then individual-device questionnaires in randomized order ([Table IGBM.2](#)). Details of the questionnaires are in Section [9.10](#). The Untrained User will be given a device-specific questionnaire only if they attempted to administer that device. For example, there will be no questionnaire for a simulation if insulin was wrongly administered instead of the glucagon device, or if no attempt was made to administer a device. Similarly, Untrained Users will be given the comparative questionnaire only if they attempted to administer both NG and GEK devices during the respective simulations.

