4.2 Secondary Objectives

- To test the hypothesis that more Untrained Users can successfully administer NG than GEK when treating a simulated episode of severe hypoglycemia.
- To compare the average time to successfully administer NG, compared with GEK, for trained and untrained users.
- To compare percentages of users who complete critical administration steps for both NG and GEK, for trained and untrained users.
- To assess the number of simulations that result in successful administration of NG.
- To assess whether, overall and for trained users, persons with diabetes (PWDs) and untrained users, one device (NG or GEK) is preferred over the other.
- To assess overall, and for trained users, PWDs and untrained users, ease of use of both devices (NG and GEK).

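### SAP 9.5 t-tests administration time with failed simulations pooled in, but the endpoint is time to successful administration and no rule gives the time a failure contributes

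*SAP*

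**What the plan says.** Protocol Section 4 (Table IGBM.1) defines the time endpoint as "The time taken by Trained Users and Untrained Users to successfully administer NG or GEK (complete dose delivered and all critical steps completed"), measured by site staff. SAP 4.2 sets the objective "To compare the average time to successfully administer NG, compared with GEK, for trained and untrained users", and the endpoint list in SAP 9.5 repeats "The time taken by Trained Users and Untrained Users to successfully administer NG or GEK".

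SAP 9.5 then plans four time comparisons: paired t-tests of NG against GEK within each cohort, and two-sample t-tests of Trained against Untrained Users within each device. On the data to be used it says: "This analysis, using descriptive statistics and the appropriate t-test, will be assessed for successful and unsuccessful administration combined, as well as successful administration only". It also plans a Kaplan-Meier plot of successful administration times, without a censoring rule.

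On what is timed, Protocol 5.1.3.1 has Part A staff assess success "and the time taken to administer a dose". Protocol 5.1.3.2 has Part B staff assess "time to successful administration (if this occurred within the allotted time"). Protocol 5.1.3.3 starts the clock when the device is found and ends the simulation after roughly 15 minutes, but does not make that end the time of a failure. SAP 13.2 on missing data concerns listings only.

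Protocol 10.3 planned the same pooled and success-only time comparisons with descriptive statistics. SAP Section 11 declares no changes from the protocol's analyses, while SAP Section 3 undertakes to identify substantial differences.

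**The concern.** A pooled t-test needs a time for each simulation it includes. For a failed one this could be when the user stopped, when an incomplete dose was given, the end of the simulation, or missing. The choice matters little if failures are rare and balanced. Here the plan expects them to be common and concentrated on one device, so the pooled NG versus GEK result could move in either direction according to a rule that is not written down, and a reader could take it as the answer to the time-to-success objective. SAP 9.5 does not say which of its two versions is the main one.

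The two parts may also time different things. If Part B failures have no recorded time and Part A failures do, the pooled Trained versus Untrained tests do not compare like with like.

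**Working it through.** **Inputs from SAP Section 7 (also Protocol 10.1).** 26 users per cohort; "It is assumed that the percentages of successful dosing of NG and GEK will be 90% and 50%, respectively"; "a proportion of discordant pairs of 45% is assumed"; two-sided alpha 0.05; stated power 90%.

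**Pair probabilities.**
- NG succeeds, GEK fails: (0.45 + 0.40)/2 = 0.425
- GEK succeeds, NG fails: (0.45 − 0.40)/2 = 0.025
- Both succeed: 0.90 − 0.425 = 0.475
- Both fail: 1 − 0.425 − 0.025 − 0.475 = 0.075

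**The plan's own figure.** With these cells and n = 26, McNemar power is 91.1% by the Connor normal approximation and 90.8% by the exact test. The stated 90% reproduces, so the cells are a fair basis for what follows.

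**Expected counts per cohort.**
- GEK failures: 26 × 0.50 = 13; NG failures: 26 × 0.10 = 2.6
- Both succeed: 26 × 0.475 = 12.35 pairs (5th to 95th binomial percentile 8 to 17)
- At least one failure: 26 − 12.35 = 13.65 pairs, of which 26 × 0.425 = 11.05 are GEK failures alone

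**Effect on the pooled mean.** Let f be the length of a failed attempt divided by that of a successful one (assumed the same for both devices), with equal success times on both devices. The pooled GEK/NG ratio of means is (0.5 + 0.5f)/(0.9 + 0.1f).
- f = 0.5: 0.75/0.95 = 0.79
- f = 1: 1.00
- f = 1.5: 1.25/1.05 = 1.19

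The pooled difference of means, GEK minus NG, is 0.4 × (f − 1) × mean success time. With an assumed log-normal median of 60 s and log SD 0.6, the mean is 60 × exp(0.18) = 71.8 s, so the difference is −14.4 s at f = 0.5 and +14.4 s at f = 1.5.

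**Effect on the paired t-test.** Simulation of 20,000 trials of 26 users; log-normal times as above, within-user correlation 0.3, 900 s cap, success independent of speed, no speed difference among successes. All time inputs are assumptions, and every failure is given a time.

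| Data analysed | Significant at 5% | Apparent direction |
|---|---|---|
| Pooled, f = 0.5 | about 28% | GEK faster |
| Pooled, f = 1 | about 5% | neither |
| Pooled, f = 1.5 | about 17% | GEK slower |
| Success-only pairs | about 4% | neither |

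Over log SD 0.4 to 0.8 and correlation 0 to 0.6, the f = 0.5 figure ranges over about 14 to 61% and the f = 1.5 figure over about 9 to 46%.

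**Success-only data.** The by-device summaries use about 26 × 0.90 = 23.4 NG and 13 GEK times. The paired test can use only the 12 or so users who succeed with both devices. With 12 pairs the 95% CI half-width is t(0.975, 11)/√12 = 0.64 SD of the within-user difference. The SAP calls 50% a best case for GEK; at the 12.5% complete-success rate it cites, at most 26 × 0.125 = 3.25 pairs would remain.

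**The case against.** The endpoint is already analysed. Every time comparison in SAP 9.5 is also run on successes alone, which matches the endpoint, and that analysis holds its size in the simulation. This stands, and it limits the point to the pooled tests.

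The pooled view has a documented purpose. Protocol 5.1.2 lists speed of delivering a dose separately from success, and Protocol 10.3 planned the pooled view descriptively. Pooled attempt time can be read as a question of its own. This also stands, with two consequences. First, a reader might infer from 28% and 17% that the pooled test has an inflated type I error. It does not: at f = 0.5 or 1.5 mean attempt times really do differ, so these are rates of detecting that difference and then misreading it as time to success. Second, failure imbalance alone does not create the effect. At f = 1, with the same imbalance, about 5% of trials are significant. Failed attempts must also differ materially in length, and neither document says that they do.

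A more dramatic reading enters every failure at 900 s, which makes about 95% of pooled tests significant. No passage assigns that value, so it cannot be attributed to the plan.

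Not every failure need have a time. Where insulin was given or no attempt was made, there is no glucagon administration to time, and those simulations may have been meant as missing. If half of failures were of that kind (an assumption), the 28% and 17% fall to about 12% and 9%. The table shells or operations manual, which are not among the documents, may hold a rule. A rule that decides which data enter a test still belongs in the SAP.

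Finally, Protocol 5.1.3.2 may simply be loosely worded, since pooled times are planned for both cohorts. That is possible, and the passages need reconciling for that reason.

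**Conclusion.** The point holds for the pooled t-tests. They do not address the stated endpoint, the time contributed by a failure is undefined, and at the plan's rates about half the pairs (13.65 of 26) contain a failure, mostly on GEK. The counts follow from SAP Section 7. The direction and size of any distortion do not: they depend on how long failed attempts last, which is assumed here.

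A reader might infer that the success-only paired t-test is defective because it loses half the pairs. The documents do not support that. The test is valid for users who succeed with both devices; it is conditional on that and less precise, and readers should see the number of pairs.

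The t-tests are an addition to the protocol's descriptive plan that SAP Section 11 does not list. That is a documentation gap. The primary McNemar comparison and the secondary comparison of success in Untrained Users are not affected.

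**What to change.** - **Endpoint analysis.** Name the success-only analysis as the analysis of time to successful administration. Label its paired t-test as conditional on success with both devices and show the number of pairs. Report failed-attempt times separately and descriptively, in place of the pooled t-tests.
- **Kaplan-Meier plot.** Draw it as cumulative success on all simulations. Keep every failure, including wrong-drug and no-attempt simulations, as a non-success to a fixed limit at the end of the simulation, so that each curve levels off at its success rate. State the time origin, how users who never find the device enter, and whether the 15 minutes run from entering the room or from finding the device.
- **Consistency.** Reconcile the time recorded in Part A (Protocol 5.1.3.1) with that in Part B (Protocol 5.1.3.2), and list the added t-tests in SAP Section 11.
- **Optional.** Report the proportion successful by fixed times taken from the SAP's own categories, with paired 95% intervals.

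The cost is SAP wording and a few lines of code; success status and successful times are already planned data. No passage says that the end of each simulation is recorded, so the fixed limit must be written down. The downside is slightly more analysis work and a curve that mixes success with speed and partly overlaps the McNemar comparison. Mean time in seconds remains available from the success-only summaries. SAP Section 3 requires sign-off before the first simulation, so the rule should be set by then.
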